9.1.7. Confirmed HZ episodes (for HZ/su and mRNA-1273 booster cohort only)	44
9.1.8. COVID-19 cases	44
9.1.9. Pregnancies	45
9.1.10. Medical Device Deficiencies	45
10. SAFETY ANALYSIS FOR SAFETY REVIEW TEAM REVIEW	45
11. INTERIM ANALYSIS	45
12. CHANGES IN THE PLANNED ANALYSIS	46
13. REFERENCES	47
14. APPENDICES	48
14.1. SCHEDULE OF ACTIVITIES	48
14.2. ADDITIONAL POWER DETAILS.....	48
14.2.1. HZ COHORT	48
14.2.2. FLU COHORT	51

Amendment Summary of Changes

This document is an amendment to statistical analysis plan version 1 dated December 3, 2021. A table of changes is presented below.

Revision Chronology:	
Version	Date
Original	03DEC2021
Amendment No. 1	Refer to Last Signature

Updates include:

- Updates to the interim analysis (IA) details due to immunogenicity data not being available at the time of the IA.
- Additional non-evaluable rates provided in an appendix to demonstrate the power for situations where the non-evaluable rate is >10%.
- Clarifications that the PPS is evaluated per vaccine (HZ/su, Flu D-QIV, and mRNA-1273)
- Additional summaries added for new subgroups safety, reactogenicity and immunogenicity endpoints and for the Exposed set in immunogenicity endpoints.
- Clarifications added regarding actual data and analysis details that deviated from protocol.
- Other minor edits for clarification.

List of Abbreviations

AE	adverse event
AESI	adverse event of special interest
ANCOVA	analysis of covariance
ATC	Anatomical Therapeutic Chemical
BMI	Body mass index
CBER	Center for Biologics Evaluation and Research
CI	Confidence interval
COVID-19	coronavirus disease 2019
CRF	case report form
DBF	database freeze
ECG	electrocardiogram
FAS	full analysis set
Flu D-QIV	quadrivalent seasonal influenza vaccine
FluD-	group receiving the mRNA-1273 booster dose co-administered with the Flu D-QIV dose
QIVCoAd	group receiving the mRNA-1273 booster dose followed by the Flu DQIV dose
FluD-	group receiving the mRNA-1273 booster dose followed by the Flu DQIV dose
QIVSeq	glycoprotein E
gE	glycoprotein E
GI	gastrointestinal
GMC	geometric mean concentration
GMT	geometric mean titer
HI	hemagglutinin inhibition
HZ	herpes zoster
HZ/su	Herpes Zoster subunit vaccine
HZ/suCoAd	group receiving the mRNA-1273 booster dose co-administered with first dose of HZ/su
HZ/suSeq	group receiving the mRNA-1273 booster dose followed by the first dose of HZ/su
IA	interim analysis
IMC	intercurrent medical condition
IRT	interactive response tool
LLOQ	lower limit of quantification
MedDRA	Medical Dictionary for Regulatory Activities
MGFI	mean geometric increase
MPL	3-O-desacyl-4'-monophosphoryl lipid A
mRNA	messenger ribonucleic acid
mRNA-1273	mRNA-based vaccine against COVID-19
PCR	Polymerase chain reaction
pIMD	potential immune mediated disease
PPS	per protocol set
PT	preferred term
RBD	Receptor binding domain
SAE	serious adverse event

SAP	statistical analysis plan
SARS-CoV-2	Severe Acute Respiratory Syndrome Coronavirus 2
SOC	system organ class
SCR	seroconversion rate
S-protein	spike protein
SPR	seroprotection rate
SRT	safety review team
su	subunit
ULOQ	Upper limit of quantification
VRR	vaccine response rate
VZV	varicella zoster virus
WHO	World Health Organization
YOA	years of age

1. Introduction

The purpose of this study is to evaluate the safety and immunogenicity of GlaxoSmithKline Biologicals SA's (GSK's) herpes zoster (HZ) subunit (su) vaccine (hereafter referred to as HZ/su) and quadrivalent seasonal influenza vaccine (hereafter referred to as Flu D-QIV) when administered sequentially or simultaneously with ModernaTX, Inc.'s (hereby referred to as Moderna) messenger ribonucleic acid (mRNA)-based vaccine booster (hereafter referred to as mRNA-1273 booster) against coronavirus disease 2019 (COVID-19).

This statistical analysis plan (SAP) is developed to provide the details of the planned statistical methodology for both the interim analysis and final analysis (used for the preparation of final study report after database lock). It is based upon the final protocol amendment version date 21 September 2021. The SAP is finalized prior to the interim analysis (IA) start. The SAP amendment is finalized prior to final database lock. Major changes in the analysis that are made after database lock will be documented in the Clinical Study Report along with the rationale and other details.

2. Objectives

2.1. Primary Objective and Endpoints

Objectives	Endpoints

• To demonstrate the non-inferiority of humoral immunogenicity of 2 doses of HZ/su when the first dose of HZ/su is co-administered with the mRNA-1273 booster dose compared to HZ/su administered alone.	
• Anti-glycoprotein E (gE) antibody concentrations expressed as group geometric mean concentration (GMC) ratio at 1 month post-dose 2 of HZ/su (at Week 14 for HZ/suSeq, at Week 12 for HZ/suCoAd).

• To demonstrate non-inferiority of humoral immunogenicity of 1 dose of mRNA-1273 booster when the first dose of HZ/su is co-administered with the mRNA-1273 booster dose compared to mRNA-1273 booster dose administered alone.	
• Anti-S Protein antibody concentrations expressed as group GMC ratio at 1 month post mRNA-1273 booster dose (at Week 4 for HZ/suSeq and HZ/suCoAd).

• To demonstrate non-inferiority of humoral immunogenicity of 1 dose of Flu D-QIV when co-administered with mRNA-1273 booster dose compared to Flu D-QIV administered alone based on geometric mean titer (GMT) of Flu D-QIV antibody titers against the 4 influenza strains.	
• Anti-hemagglutinin inhibition (HI) antibody titers expressed as group GMT ratio against the 4 influenza strains included in Flu D-QIV at 1 month post Flu D-QIV (at Week 6 for FluD-QIVSeq, at Week 4 for FluD-QIVCoAd).

• To demonstrate non-inferiority of humoral immunogenicity of 1 dose of mRNA-1273 booster when co-administered with Flu D-QIV compared to mRNA-1273 booster dose administered alone.	
• Anti-S Protein antibody concentrations expressed as group GMC ratio at 1 month post mRNA-1273 booster dose (at Week 4 for FluD-QIVSeq and FluD-QIVCoAd).

2.2. Secondary Objectives and Endpoints

Objectives	Endpoints
Secondary – Immunogenicity	

 To demonstrate the non-inferiority of humoral immunogenicity of 1 dose of Flu D-QIV vaccine when co-administered with mRNA-1273 booster dose compared to Flu D-QIV administered alone based on seroconversion rate (SCR) difference of Flu D-QIV HI antibody titers against 4 influenza strains. 	
 Anti-HI antibody SCR difference against the 4 influenza strains at 1 month post Flu D-QIV (at Week 6 for FluD-QIVSeq, at Week 4 for FluD-QIVCoAd).

 To characterize the anti-gE humoral immunogenicity at pre-vaccination and at 1 month post-dose 2 of HZ/su. 	
 Seropositivity rate with exact 95% confidence interval (CI) at pre-vaccination (at Day 1 for HZ/suCoAd, at Week 2 for HZ/suSeq) and at 1 month post-dose 2 of HZ/su (at Week 14 for HZ/suSeq, at Week 12 for HZ/suCoAd). Anti-gE antibody concentrations expressed as GMC with 95% CI at pre-vaccination (at Day 1 for HZ/suCoAd, at Week 2 for HZ/suSeq) and at 1 month post-dose 2 of HZ/su (at Week 14 for HZ/suSeq, at Week 12 for HZ/suCoAd). Vaccine response rate (VRR) with exact 95% CIs at 1 month post-dose 2 of HZ/su (at Week 14 for HZ/suSeq, at Week 12 for HZ/suCoAd). Mean geometric increase (MGI) from pre-vaccination with 95% CI at 1 month post-dose 2 of HZ/su (at Week 14 for HZ/suSeq, at Week 12 for HZ/suCoAd).

Objectives	Endpoints
Secondary – Immunogenicity	

 To characterize the humoral immunogenicity of mRNA-1273 booster dose. 	
 Anti-S Protein antibody concentrations expressed as GMC with 95% CI at pre-vaccination (Day 1) and 1 month post mRNA-1273 booster dose (at Week 4 for all groups). MGI from pre-vaccination with 95% CI at 1 month post mRNA-1273 booster dose (at Week 4 for all groups).

 To evaluate the humoral immunogenicity of Flu D-QIV. The assessment of seroprotection rate (SPR) and SCR will be based on Center for Biologics Evaluation and Research's (CBER) criteria. 	
 Anti-HI antibody titers against the 4 influenza strains included in Flu D-QIV expressed as GMTs with 95% CI at pre-vaccination and at 1 month post Flu D-QIV (at Week 6 for FluD-QIVSeq, at Week 4 for FluD-QIVCoAd). SPR with exact 95% CI at pre-vaccination and at 1 month post Flu D-QIV (at Week 6 for FluD-QIVSeq, at Week 4 for FluD-QIVCoAd), overall and by age category (18-64 and ≥ 65 years of age [YOA]). Seropositivity rate with exact 95% CI at pre-vaccination and at 1 month post Flu D-QIV (at Week 6 for FluD-QIVSeq, at Week 4 for FluD-QIVCoAd). MGI with 95% CI from pre-vaccination at 1 month post Flu D-QIV (at Week 6 for FluD-QIVSeq, at Week 4 for FluD-QIVCoAd). SCR with exact 95% CI from pre-vaccination at 1 month post Flu D-QIV (at Week 6 for FluD-QIVSeq, at Week 4 for FluD-QIVCoAd), overall and by age category (18-64 and ≥ 65 YOA).

Objectives	Endpoints
Secondary – Safety/Reactogenicity	

• To evaluate the safety and reactogenicity following administration of HZ/su, Flu D-QIV and mRNA-1273 booster dose, up to 30 days post-last vaccination and during the whole post-vaccination follow-up period.	
• Solicited adverse events (AEs): Number and percentage of participants reporting each solicited local AE and each solicited systemic AE within 7 days (Days 1-7) after each dose and overall.• Unsolicited AEs:
○ Number and percentage of participants reporting unsolicited AEs within 14 days (Days 1-14) after each vaccination visit and overall after any vaccination visit for all groups.○ Number and percentage of participants reporting unsolicited AEs within 30 days (Days 1-30) after each vaccination visit and overall after any vaccination visit for all groups.• Serious adverse events (SAEs):
○ Number and percentage of participants reporting SAEs from first dose up to 30 days post-last dose within each group.○ Number and percentage of participants reporting SAEs from first dose to study end.

	
• Potential immune mediated diseases (pIMDs) in HZ/su and mRNA-1273 booster cohort only:
○ Number and percentage of participants reporting of pIMDs from first dose up to 30 days post-last dose within each group.○ Number and percentage of participants reporting pIMDs from first dose to study end.• Adverse events of special interest (AESIs):
○ Number and percentage of participants reporting AESIs from first dose up to 30 days post-last dose within each group.○ Number and percentage of participants reporting AESIs from first dose to study end.• Suspected HZ episodes in HZ/su and mRNA-1273 booster cohort only: Number and percentage of participants reporting clinically suspected HZ episodes from first dose to study end.• COVID-19 cases: Number and percentage of participants meeting case definitions of COVID-19 from first dose to study end.
--	---

2.3. Exploratory Objectives and Endpoints

Objectives	Endpoints

• To evaluate the incidence of lab-confirmed HZ episodes following administration of HZ/su during the whole follow-up period.	
• Confirmed HZ cases in HZ/su and mRNA-1273 booster cohort only: Number and percentage of participants with polymerase chain reaction (PCR) confirmed HZ episodes from first vaccination to study end.

Objectives	Endpoints

• To characterize the anti-gE humoral immunogenicity at 1 month post-dose 1 of HZ/su.	
• Seropositivity rate with exact 95% CI at 1 month post-dose 1 of HZ/su (at Week 6 for HZ/suSeq, at Week 4 for HZ/suCoAd).• Anti-gE antibody concentrations expressed as GMC with 95% CI at 1 month post-dose 1 of HZ/su (at Week 6 for HZ/suSeq, at Week 4 for HZ/suCoAd).• VRR with exact 95% CIs at 1 month post-dose 1 of HZ/su (at Week 6 for HZ/suSeq, at Week 4 for HZ/suCoAd).• MGI from pre-vaccination with 95% CI at 1 month post-dose 1 of HZ/su (at Week 6 for HZ/suSeq, at Week 4 for HZ/suCoAd).

• To further evaluate the immune response to the mRNA-1273 booster vaccine via neutralizing antibody titers in a sub-cohort of participants in all study groups.	
• GMT with 95% CIs of SARS-CoV-2 neutralizing antibody titers in a sub-cohort of participants in each study group at pre-vaccination and at 1 month post mRNA-1273 booster dose (Week 4 for all groups).

• To evaluate further SARS-CoV-2/mRNA-1273 immune responses during the study.	
• GMCs with 95% CI of anti-receptor binding domain (RBD) protein antibodies at pre-vaccination and 1 month post mRNA-1273 booster dose (at Week 4 for all groups).• Anti-nucleocapsid (N) protein seroconversion rate with exact 95% CI from pre-vaccination to 1 month post mRNA-1273 booster dose (at Week 4 for all groups).

[figure not shown]
3. Investigational Plan

3.1. Overall Study Design and Plan

This study is a Phase III, randomized, open-label, controlled, multicenter US-based study to evaluate the immune response and safety of both HZ/su in healthy adults 50 YOA and older and Flu D-QIV in healthy adults 18 YOA and older when administered sequentially or co-administered with mRNA-1273 booster vaccination.

The study will be conducted in the U.S. and will enroll participants in 2 main study cohorts, HZ/su with mRNA-1273 booster vaccine administered sequentially or concomitantly and Flu D-QIV with mRNA-1273 booster vaccine administered sequentially or concomitantly, hereafter entitled HZ/su and mRNA-1273 booster cohort and Flu D-QIV and mRNA-1273 booster cohort, respectively (Figure 1).

Figure 1 Study design overview

EOS = end of study, telephone contact at 24 weeks post last vaccine dose; N = number of participants enrolled and randomized; PLD = post last dose

*Safety Review Team evaluation of 7 days post-dosing after Visit 1 safety data for initial 10% vaccinated in the HZ/suCoAd group and 5% vaccinated in the FluD-QIVCoAd group prior to full randomization in the respective cohorts

Potential participants will be triaged initially to either study cohort (HZ/su and mRNA-1273 booster, Flu D-QIV and mRNA-1273 booster) based upon criteria such as seasonal influenza vaccine availability, known eligibility criteria (such as age and vaccination history), and current study enrollment status. Subsequently, enrolled (i.e., having signed an informed consent form) and eligible participants in each cohort will be randomized in a 1:1 ratio to each of the 2 study groups within each cohort (Table 1).

Table 1 Study groups, intervention, and blinding

Cohort	Study Groups	Number of Randomized Participants	Age	Study Interventions	Blinding
					Visit 1 → Phone Contact 2 (Open-label)*
HZ/su and mRNA1273 Booster	HZ/suSeq	273	≥50 years**	mRNA-1273 booster HZ/su	x
	HZ/suCoAd	273			
Flu D-QIV and mRNA-1273 Booster	FluD-QIVSeq	500	≥18 years**	mRNA-1273 booster Flu D-QIV	x
	FluD-QIVCoAd	500			

*This is an open-label study; however, the specific participant vaccination schedule (sequential or coadministration) will be randomly assigned within each cohort.

** Randomization will be set to ensure at least 69 participants per group will be ≥ 70 YOA in the HZ/su and mRNA-1273 booster cohort and **to target** at least 75 participants ≥ 65 YOA **per group** in the Flu D-QIV and mRNA-1273 booster cohort. **(Amended 21 September 2021)**

- In the HZ/su and mRNA-1273 booster cohort, 546 participants will be randomized in a 1:1 ratio so that 273 participants are assigned to each study group. The first group (HZ/suSeq group) will receive the mRNA-1273 booster dose followed approximately 2 weeks later by the first dose of HZ/su, while the second group (HZ/suCoAd group) will receive the mRNA-1273 booster dose co-administered with the first dose of HZ/su. All participants in the HZ/suSeq group and the HZ/suCoAd group will receive the second dose of HZ/su approximately 2 months after the first HZ/su dose. Randomization into each group will be stratified by age (50 to 59, 60 to 69, and ≥ 70 YOA) and will be set to ensure a minimum number of 138 participants are assigned to the ≥ 70 YOA stratum, 69 participants to each group.
- In the Flu D-QIV and mRNA-1273 booster cohort, 1000 participants will be randomized in a 1:1 ratio so that 500 participants are assigned to each study group. The first group (**FluD-QIVSeq group**) will receive the mRNA-1273 booster dose followed approximately 2 weeks later by the Flu D-QIV dose, while the second group (**FluD-QIVCoAd group**) will receive the mRNA-1273 booster dose co-administered with the Flu D-QIV dose. Randomization into each group will be stratified by age (18 to 64 and ≥ 65 YOA) and will be set to target a minimum number of 150 participants are assigned to the ≥ 65 YOA stratum, 75 participants to each group.

All study participants will be followed for safety until 6 months post the last dose of the study vaccine with the total duration of study participation approximately 34 and 26 weeks in the HZ/su and mRNA-1273 booster cohort and Flu D-QIV and mRNA-1273 booster cohort, respectively.

3.2. Study Endpoints

Please refer to Section 2 of this SAP.

3.3. Treatments

Table 2 Study interventions administered

Study Intervention Name:	HZ/su		Flu D-QIV	mRNA-1273
Product Name:	VZV gE	AS01B	Flu D-QIV 2021-2022 NH	COVID-19 mRNA Vaccine
Study intervention Formulation:	VZV gE (50 µg)	AS01B: QS-21 (50 µg), MPL (50 µg), liposomes; water for injections q.s. 0.5 mL	Flu Quadrivalent Influenza vaccine 15 µg per strain*/dose	100 µg per dose (embedded in SM-102 lipid nanoparticles); water for injections q.s. 0.5 mL
Formulation Dose Form:	Powder for suspension for injection	Suspension for injection	Suspension for injection	Dispersion for injection
Presentation:	Vial	Vial	Syringe	Vial
Product Category:	Biologic		Combination product	Biologic
Type:	Study Vaccine		Study Vaccine	Study Vaccine
Route of Administration:	Intramuscular injection		Intramuscular injection	Intramuscular injection
Administration Site:	Left deltoid		Left deltoid	Right deltoid
Number of Doses to be Administered:	2		1	1
Volume to be Administered**:	0.5 mL		0.5 mL	0.25 mL
Packaging and labeling:	Refer to the Pharmacy Manual			
Manufacturer:	GSK	GSK	Moderna	

HZ/su = herpes zoster subunit vaccine; VZV = varicella zoster virus; gE = glycoprotein E; AS01B = adjuvant system 01B; NH = North hemisphere; QS-21 = Quillaja saponaria Molina, fraction 21 (Licensed by GSK from Antigenics Inc, a wholly owned subsidiary of Agenus Inc., a Delaware, USA corporation); MPL = 3-O-desacyl-4'-monophosphoryl lipid A; q.s. = *quantum satis*

* A/Victoria/2570/2019 (H1N1), IVR-215 (15 µg HA); A/Tasmania/503/2020 (H3N2), IVR-221 (15 µg HA);

B/Washington/02/2019 (15 µg HA); B/Phuket/3073/2013 (15 µg HA); Water for injections q.s. 0.5 mL

**Refer to the Pharmacy Manual for more details.

4. General Statistical Considerations

Data will be displayed in all listings sorted by treatment group and cohort.

Continuous data will be described using descriptive statistics (n, mean, standard deviation, median, minimum, and maximum). **Categorical data** will be described using the participant count and percentage for each category.

For the **summary statistics** of all numerical variables unless otherwise specified, minimum and maximum will be displayed to the same level of precision as reported. Mean, Confidence Interval (CI) and median will be displayed to one level of precision greater than the data collected. Standard deviation / standard error will be displayed to two levels of precision greater than the data collected.

When count data are presented, percentages/ratio will be rounded to one decimal place. If count is 0 the percentage will be presented as 0.0%. If percentages are 100%, no decimal will be displayed. CI will be presented to two decimal places for proportion/ratio, wherever applicable. A row denoted “Missing” will be included in count tabulations where specified on the shells to account for dropouts and missing values.

The denominator for all percentages will be the number of participants with non-missing values of corresponding parameter in that treatment group or cohort within the analysis population of interest, unless otherwise specified.

Unless otherwise specified, **baseline** will be defined as the last non-missing evaluation prior to first vaccine administration on Day 1, except the HZ/su and Flu D-QIV baseline immunogenicity in participants in the sequential groups which will have Week 2 as baseline.

Study day: If the event is after the first vaccine administration date then the study day will be calculated as assessment date – date of first vaccine administration + 1 else if event is prior to the first vaccine administration date then it will be calculated as assessment date – date of first vaccine.

Calculation regarding antibody concentrations/titers: Antibody values reported as below the lower limit of quantification (LLOQ) will be replaced by $0.5 \times \text{LLOQ}$. Values that are greater than the upper limit of quantification (ULOQ) will be converted to the ULOQ. Missing results will not be imputed.

All statistical analyses will be performed using SAS[®] software version 9.4 or later.

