4.1. Sample Size

Assumptions used for the sample size calculations come from data available from prior studies ZOSTER-004 (117036), ZOSTER-042 (116887), ZOSTER-035 (116889), ZOSTER-048 (201198), ZOSTER-059 (204487), FLU D-QIV-008 (114269), FLU DQIV-010 PRI (117276), and EXPLO-CRD-004, as well as preliminary mRNA-1273 Phase I and Phase II data [Jackson, 2020; Chu, 2021].

After final assay evaluations and validations, should the primary mRNA-1273 endpoint be replaced by SARS-CoV-2 neutralizing antibody titers, the same assumptions will be made since the standard deviation used for calculations was at the upper range of what has been

observed for both endpoints; thus, the sample sizes presented below will remain for each cohort.

The type I error to be maintained is 0.025 (one-sided) for each study cohort (HZ/su and mRNA-1273 booster, Flu D-QIV and mRNA-1273 booster). Study success will be evaluated separately for each cohort. For the HZ/su and mRNA-1273 booster cohort, non-inferiority must be achieved for both hypothesis 1 and hypothesis 2, see Section 8.1. For the Flu D-QIV and mRNA-1273 booster cohort, success must be achieved for both hypothesis 3 and hypothesis 4; see Section 8.1.

A total of 1546 participants will need to be enrolled and randomized between the 2 cohorts.

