4.1.1 Sample size for HZ/su and mRNA-1273 study cohort

The global power considers meeting the primary objectives in the HZ/su and mRNA-1273 booster cohort with 245 evaluable participants in the HZ/suCoAd and HZ/suSeq groups, the global power is approximately 90%. A GMC ratio of 1.1 between HZ/suSeq and HZ/suCoAd is assumed. Assuming 10% of the participants randomized are non-evaluable (e.g. due to drop out/protocol violation), approximately 546 participants will need to be randomized (273 participants each in the HZ/suCoAd and HZ/suSeq groups).

If the dose of mRNA-1273 booster is adjusted while the study is ongoing, the sample size will be compensated in this cohort to ensure that there are enough evaluable participants in each group. In such a case, the details of the sample size re-estimation requirements for the HZ/su and mRNA-1273 study cohort will be provided explicitly in a subsequent protocol amendment.

Sample size calculations for the HZ/su and mRNA-1273 booster study cohort can be found in Table 3.

Table 3 Sample size calculations for HZ/su and mRNA-1273 booster study cohort

Endpoint	Number of Evaluable Participants per Cohort	α	Standard Deviation	Reference δ Assumed	NI δ	Total β	Power
Post dose 2 HZ/su Non-inferiority* (1-sided test) – Primary Endpoint							
Post-Dose 2 GMC Ratio (Sequential vs. Co-Ad) anti-gE	245	0.025	0.35	1.1	1.5	1.1%	98.9%
mRNA-1273 booster vaccine: Non-inferiority* (1-sided test) – Primary Endpoint							
GMC Ratio (Sequential vs. Co-Ad) anti-S	245	0.025	0.45	1.1	1.5	8.9%	91.1%
Global β to show non-inferiority of the primary endpoints						~10%	
Global power for the primary endpoints							~90%

Co-Ad = co-administered; GMC = geometric mean concentration

* Pass 2019: alpha = 2.5% for HZ/su and mRNA-1273 booster GMC ratio; Non-Inferiority -Two Independent Means – Two-sample T-tests for Non-Inferiority Assuming Equal Variance

For gE and mRNA-1273 booster vaccine: non-inferiority limit = 0.176 (=log10(1.5)), reference limit = 0.0413 (=log10(1.1)).

SDs for HZ/su Dose 2 are taken from the average of the reference co-administration studies ZOSTER-004 (117036), ZOSTER-042 (116887), ZOSTER-035 (116889), ZOSTER-048 (201198), ZOSTER-059 (204487), FLU D-QIV-008 (114269), FLU D-QIV-010 PRI (117276), and EXPLO-CRD-004. SDs for mRNA-1273 booster are taken from preliminary mRNA-1273 Phase I and II data.

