8.1. Primary Immunogenicity Endpoint

Primary objectives for HZ/su and mRNA-1273 booster cohort:

Hypothesis 1: The null hypothesis for this primary objective under consideration is Upper (Limit (UL) of 95% CI for adjusted GMC ratio between HZ/suSeq group and HZ/suCoAd group for anti-gE antibody concentration at 1 month post-dose 2 of HZ/su (at Week 14 for HZ/suSeq, at Week 12 for HZ/suCoAd) is ≥ 1.5 .

Success criteria: The objective will be met if the UL of the 95% CI of the adjusted GMC ratio between HZ/suSeq and HZ/suCoAd group for anti-gE antibody concentration at 1 month post-dose 2 of HZ/su (at Week 14 for HZ/suSeq, at Week 12 for HZ/suCoAd) is < 1.5 .

Hypothesis 2: The null hypothesis for this primary objective under consideration is UL of 95% CI for adjusted GMC ratio between HZ/suSeq and HZ/suCoAd group for anti-S protein antibody concentration at 1 month post mRNA-1273 booster dose (at Week 4 for HZ/suSeq and HZ/suCoAd) is ≥ 1.5 .

Success criteria: The objective will be met if the UL of the 95% CI of the adjusted GMC ratio between HZ/suSeq and HZ/suCoAd group for anti-S protein antibody at 1 month post mRNA-1273 booster dose (at Week 4 for HZ/suSeq and HZ/suCoAd) is < 1.5 .

Primary objectives for Flu D-QIV and mRNA-1273 booster cohort:

Hypothesis 3:- The null hypothesis for this primary objective under consideration is UL of 95% CI for adjusted GMT ratio between FluD-QIVSeq and FluD-QIVCoAd group for anti-HI antibody titer at 1 month post Flu D-QIV (at Week 6 for FluD-QIVSeq, at Week 4 for FluD-QIVCoAd) is ≥ 1.5 .

Success criteria - The objective will be met if the UL of the 95% CI of the adjusted GMT ratio between FluD-QIVSeq and FluD-QIVCoAd group for anti-HI antibody titer at 1 month post Flu D-QIV (at Week 6 for FluD-QIVSeq, at Week 4 for FluD-QIVCoAd) is < 1.5 for each strain included in the Flu D-QIV vaccine.

Hypothesis 4: The null hypothesis for this primary objective under consideration is UL of 95% CI for adjusted GMC ratio between FluD-QIVSeq and FluD-QIVCoAd group for anti-S protein antibody concentration at 1 month post mRNA-1273 booster dose (at Week 4 for FluD-QIVSeq and FluD-QIVCoAd) is ≥ 1.5 .

Success criteria - The objective will be met if the UL of the 95% CI of the adjusted GMC ratio between FluD-QIVSeq and FluD-QIVCoAd group for anti-S protein antibody concentration at 1 month post mRNA-1273 booster dose (at Week 4 for FluD-QIVSeq and FluD-QIVCoAd) is <1.5.

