For anti-S Protein at 1 month post mRNA-1273 booster dose, the least square point estimate and its 95% CI of the between group GMC ratios will be computed using ANCOVA model on the log10 transformation of the concentrations to demonstrate non-inferiority of the HZ/suCoAd vs. HZ/suSeq for the HZ/su immune response. The age strata (50-59, 60-69, ≥ 70 YOA) and pre-vaccination log-transformed antibody concentrations will be included as covariates and vaccine group will be included as a fixed effect.

Pending final assay evaluations and validations prior to study specimen testing, anti-S protein may be replaced with SARS-CoV-2 neutralizing antibody titers in which case, GMT ratios will be used in the analysis described above.

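### Antibody values above the ULOQ are set to the ULOQ and analysed as exact; if post-dose values are capped, this favours non-inferiority, and no censored-data check is planned

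*SAP*

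**What the plan says.** SAP section 4 (General Statistical Considerations) has one rule for all antibody concentrations and titres: "Values that are greater than the upper limit of quantification (ULOQ) will be converted to the ULOQ". At the other end, "Antibody values reported as below the lower limit of quantification (LLOQ) will be replaced by" half the LLOQ, and missing results are not imputed. SAP Amendment 1 and the December 2021 SAP carry the same rule.

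The primary analyses in SAP 8.1.1 and 8.1.2 are ordinary least squares. For anti-S in the HZ cohort, for example, the ratio and its interval are "computed using ANCOVA model on the log10 transformation of the concentrations", with age stratum, log baseline and group in the model. Protocol 9.3.4 prespecifies the same ANCOVA. Success is defined in SAP 8.1: "The objective will be met if the UL of the 95% CI of the adjusted GMC ratio between HZ/suSeq and HZ/suCoAd group" is below 1.5, and the Flu cohort has the same rule. SAP 4.1 adds: "The type I error to be maintained is 0.025 (one-sided) for each study cohort".

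Neither document gives a ULOQ, an expected share above it, a re-dilution rule, a censored-data model or a planned count of capped values. SAP section 8 repeats the immunogenicity summaries on the Exposed Set, but those use the same capped values.

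**The concern.** A capped value is a lower bound that the model reads as a measurement. The arm with the higher true titres loses more to the cap. The tests guard against a Seq arm 1.5 times as high as CoAd, and at that boundary the Seq arm is cut more. The estimated ratio moves towards 1, and the spread in both arms shrinks as well. In a superiority test this would be conservative; here it makes a false claim of non-inferiority more likely.

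The samples are taken one month after a booster, an influenza dose or a second HZ/su dose, so the upper end of the assay range is where a problem would arise. Each cohort requires all its primary tests to pass, but that does not remove the excess: the worst case is one endpoint at 1.5 with the others well inside the margin.

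**Working it through.** **Inputs.** From SAP 4.1.1 and 4.1.2: margin log10(1.5) = 0.1761; planning ratio 1.1 (1.04 for HI); one-sided alpha 0.025; anti-gE n = 245 per group, SD 0.35; anti-S n = 245 (HZ cohort) or 450 (Flu cohort), SD 0.45; HI n = 450, SD 0.6. Assumed, because the documents do not say: normal log10 values, a ULOQ common to both arms, and the share above it.

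**The plan's own figures.** A two-sample t non-inferiority calculation (noncentral t) gives 98.9% (anti-gE), 91.1% (anti-S, n = 245), 97.8% (each HI strain) and 99.4% (anti-S, n = 450). All match SAP Tables 3 and 4, so the inputs are read correctly.

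**Effect of the cap.** For X normal with mean μ and SD σ, capped at c, with a = (c − μ)/σ:

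- E[min(X,c)] = μΦ(a) − σφ(a) + c(1 − Φ(a))
- E[min(X,c)²] = (μ² + σ²)Φ(a) − σ(μ + c)φ(a) + c²(1 − Φ(a))

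These give the capped difference d and the capped SD s. With SE = s√(2/n), the chance of declaring non-inferiority at a true ratio of 1.5 is about Φ((0.1761 − d)/SE − t), where t is the 97.5% point of the t distribution.

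**Worked case: anti-S, n = 245, 10% of all values above the ULOQ.**

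1. Put the CoAd mean at 0 and the Seq mean at 0.1761. The ULOQ then lies at c = 0.676, with 13.3% of Seq and 6.7% of CoAd above it.
2. Capped means are 0.1458 (Seq) and −0.0131 (CoAd), so d = 0.159, a ratio of 1.44 instead of 1.50.
3. Capped SD is 0.412 instead of 0.45, so SE = 0.412 × √(2/245) = 0.0372.
4. The shift is (0.1761 − 0.1590)/0.0372 = 0.46 SE.
5. Error = Φ(0.46 − 1.965) = Φ(−1.505) = 6.6%.

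**All primary endpoints, true ratio 1.5, share above the ULOQ pooled over both arms:**

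| Endpoint | 1% | 2% | 5% | 10% | 20% |
|---|---|---|---|---|---|
| Anti-S, n = 245 | 2.7% | 3.0% | 4.0% | 6.6% | 17% |
| Anti-S, n = 450 | 2.8% | 3.2% | 4.8% | 9.0% | 28% |
| Anti-gE, n = 245 | 2.8% | 3.1% | 4.5% | 8.3% | 25% |
| HI, each strain, n = 450 | 2.7% | 3.0% | 4.1% | 6.8% | 18% |

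The definition of the share matters. If 10% or 20% refers to the Seq arm alone, anti-S at n = 245 gives 5.1% or 11.4%.

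**Check with the planned model.** Simulated ANCOVA with a baseline covariate (10,000 runs per setting), with 10% of the Seq arm capped and baseline correlation 0.5, gives 5.4% for anti-S at n = 245 and 7.5% at n = 450. The two-sample shortcut does not exaggerate the problem.

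**At the planning ratio of 1.1**, for anti-S, pooled capping of 5% or 10% moves the expected ratio to 1.095 or 1.090.

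**Censored regression.** Right-censored normal regression with the same covariate (6,000 runs per setting; 5%, 10% or 20% of the Seq arm above the ULOQ) gives errors of 2.4% to 2.8% across anti-gE, anti-S (n = 245) and HI, and the mean ratio returns to 1.50. In the same runs capped ANCOVA gives 3.5%, 5.2% and 13.5% for anti-S.

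**The case against.** The strongest objection is that nothing shows the condition will arise. High titres are not the same as titres out of range. Protocol 8.1.2 describes the anti-S assay as still awaiting final evaluation and validation, so its range cannot be inferred. Neither document describes how the laboratory handles over-range sera, and results may be re-diluted before they reach the database. This stands, and it is why no single error rate can be attached to the trial.

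A reader might infer that the primary tests, as planned, run at 17% or 28% error. The documents do not support that: those cells need about a quarter of the Seq arm above the ULOQ. With no capping the error is the nominal 2.5%.

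The LLOQ rule can push the other way. With 5% of Seq above the ULOQ and 5% of CoAd below the LLOQ, the error is about 2.6% (anti-gE), 3.2% (anti-S) and 3.6% (HI). That offset requires post-vaccination values below the LLOQ, so it cannot be relied on.

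The planned maxima (SAP 8.1) and reverse cumulative curves (SAP 8.1.1 and 8.2) would reveal heavy capping. They help detection but do not correct the test.

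A reader might also conclude that the ANCOVA must give way to a censored model. That goes too far. The ANCOVA is prespecified in the protocol, a single over-range value should not switch the confirmatory model, and the censored model relies on normality and equal variance.

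**Conclusion.** The point holds in conditional form. The rule is explicit and covers every primary endpoint, it works in favour of non-inferiority, and neither document corrects for it. At a true ratio of 1.5 the excess over 2.5% is 0.2 to 0.3 points at 1% pooled capping, which is negligible. At 5% the error is 4.0% to 4.8%, and at 10% it is 6.6% to 9.0%. These figures rest on normal log10 values, a common ULOQ and assumed capped shares, and take no credit for any LLOQ offset. This is a cheap safeguard worth adding before results are seen; it is not evidence that the planned tests fail.

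**What to change.** In SAP sections 4 and 8.1:

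- Use the in-range re-diluted result where the laboratory provides one; apply the cap only otherwise.
- Report the number of values above the ULOQ by arm and endpoint.
- Keep the protocol's ANCOVA as the primary analysis.
- For each primary endpoint with capped post-dose values, prespecify a sensitivity analysis: right-censored normal (Tobit) regression on log10 values with the same group, age-stratum and baseline terms.
- Describe the non-inferiority conclusion as robust only if the upper limit from that model is also below 1.5.

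The cost is SAP wording and one extra model per affected endpoint, using a standard procedure. The model depends on normality and equal variance, and its interval is slightly wider. In simulation for anti-S (n = 245, true ratio 1.1, baseline correlation 0.5, ULOQ set where it would cap 10% of Seq at ratio 1.5), power is 96% against 98% for capped ANCOVA.
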